1.2 Display digits

Term	Definition
Percentage (%)	Percentage of patients with or percentage of adverse events, etc., or adverse drug reactions, etc.: The obtained value should be rounded off to two decimal places. Other: The obtained value should be rounded off to one decimal place.
Summary statistics (mean and standard deviation)	Mean: The raw data should be rounded off to one decimal place. Standard deviation: The raw data should be rounded off to two decimal places.
P value	The obtained value should be rounded down to three decimal places. If the value is less than 0.001 after rounding down to three decimal places, it should be displayed as “p<0.001.”

1.3 Level of significance

Two-sided 5%

1.4 Handling of test data

Test data will be handled according to the criteria shown below. If there are multiple data for the same criterion, the one with the test date being closest to the date of protocol-specified assessment should be used. If there is no difference in the number of days from the date of protocol-specified assessment, the later value should be used. For the final assessment, * however, the most recently measured value (including the one measured during the off-treatment period) after the date of the initial dose of Adcetris should be used. Values measured after 30 days after the last dose of Adcetris should not be used.

The number of days after the date of the initial dose of Adcetris is defined as 1 for the date of the initial dose of Adcetris and 0 for the day before the date of the initial dose of Adcetris.

* After 16 cycles of treatment with Adcetris (or upon discontinuation of treatment with Adcetris)

Time point for testing	Acceptable time window	Date of protocol-specified assessment
At the initial dose of Adcetris	-21 to 1 days	Date of the initial dose of Adcetris
After 1 cycle	2 to 31 days	Date of the initial dose of Adcetris + 21
After 2 cycles	32 to 52 days	Date of the initial dose of Adcetris + 42
After 3 cycles	53 to 73 days	Date of the initial dose of Adcetris + 63
After 4 cycles	74 to 94 days	Date of the initial dose of Adcetris + 84
After 5 cycles	95 to 115 days	Date of the initial dose of Adcetris + 105
After 6 cycles	116 to 136 days	Date of the initial dose of Adcetris + 126
After 7 cycles	137 to 157 days	Date of the initial dose of Adcetris + 147

Time point for testing	Acceptable time window	Date of protocol-specified assessment
After 8 cycles	158 to 178 days	Date of the initial dose of Adcetris + 168
After 9 cycles	179 to 199 days	Date of the initial dose of Adcetris + 189
After 10 cycles	200 to 220 days	Date of the initial dose of Adcetris + 210
After 11 cycles	221 to 241 days	Date of the initial dose of Adcetris + 231
After 12 cycles	242 to 262 days	Date of the initial dose of Adcetris + 252
After 13 cycles	263 to 283 days	Date of the initial dose of Adcetris + 273
After 14 cycles	284 to 304 days	Date of the initial dose of Adcetris + 294
After 15 cycles	305 to 325 days	Date of the initial dose of Adcetris + 315
After 16 cycles	326 to 346 days	Date of the initial dose of Adcetris + 336

2.0 Patient Disposition (Patient Disposition Diagram)

(1) Analysis set to be used

Patients registered to this specified drug-use survey

(2) Data to be analyzed

Data to be analyzed includes the numbers of patients registered, institutions with patients registered, patients whose case report forms are available/not available, fixed/non-fixed patients, patients included in/excluded from the safety analysis set, and patients included in/excluded from the efficacy analysis set.

For the number of institutions with patients registered, the same institutions with different departments should not be counted more than once.

For patients whose case report forms are not available, the number of patients by reason for unavailability and the total number of patients will be calculated.

For patients excluded from the safety/efficacy analysis set, the number of patients by reason for exclusion and the total number of patients will be calculated.

It will be determined as follows whether patients meeting the following criteria should be included or excluded:

Criterion	Registration	Safety evaluation	Efficacy evaluation
Duplicate registration (of the same patient) [found afterwards]	×	×	×
Non-primary disease	○	○	×
Adcetris has never been administered [found afterwards]	×	×	×
No definite safety evaluation results are available	○	×	×
No definite efficacy evaluation results are available	○	○	×
No case report form is available	○	×	×

○: Included, ×: Excluded

(3) Figure/table number

Figure 2.0 and Table2.0

3.0 Patient Demographics and Baseline Characteristics

(1) Analysis sets to be used

Safety analysis set, safety analysis set (Hodgkin’s lymphoma), and safety analysis set (anaplastic large-cell lymphoma)

(2) Data to be analyzed

For each data item, patients will be stratified into the following categories, and the number and frequency of patients will be calculated:

Data item	Category
Sex	Male or female
Age	Summary statistics
	<18 years, 18 to 39 years, 40 to 64 years, 65 to 74 years, or ≥75 years
	<18 years, 18 to 64 years, 65 to 74 years, or ≥75 years
Disease duration	<1 year, <1 to 3 years, <3 to 5years, ≥5 years, or unknown
Diagnosis	Hodgkin’s or anaplastic large-cell lymphoma or other
Status	Relapsed/refractory, or new-onset
CD30	Positive, negative, or not measured
Site(s) of involvement	Lymph node, spleen, liver, lung, bone, central nerve, bone marrow, skin, and/or other
ALK (for patients with anaplastic large-cell lymphoma)	Positive, negative, or unknown
Clinical stage	I, II, III, IV, or unknown
B symptoms	Absent or present
ECOG Performance Status	0, 1, 2, 3, or 4
Therapeutic category	Outpatient or inpatient
Hypersensitivity disposition	Absent, present, or unknown
Specific hypersensitivity disposition(s)	Medications, food allergy, and/or other
HCV antibody	Negative, positive, or unknown
HBs antigen	Negative, positive, or unknown
HBs antibody	Negative, positive, or unknown
HBV DNA	Negative, positive, or unknown
Past history of pulmonary disorders	Absent or present
Concurrent pulmonary disorders	Absent or present

Data item	Category
Past history of malignant tumours	Absent or present
Concurrent malignant tumours	Absent or present
Past history (other than pulmonary disorders and malignant tumours)	Absent, present, or unknown
Concurrent illness (other than pulmonary disorders and malignant tumours)	Absent or present
Specific concurrent illness(es) (other than pulmonary disorders and malignant tumours)	Diabetes mellitus, hypertension, dyslipidaemia, hyperuricaemia, hepatic disease(s), renal disease(s), infections, peripheral nerve disorders, and/or other
Concurrent renal disorders	Absent or present
Grade of hepatic disorder (CTCAE grade based on AST and ALT levels)	None, Grade 1, Grade 2, or \geq Grade 3
Concurrent renal disorders	Absent or present
Grade of renal disorder (CTCAE grade based on serum creatinine)	None, Grade 1, Grade 2, or \geq Grade 3
Weight	Summary statistics
	<40 kg, <40 to 50 kg, <50 to 60 kg, <60 to 70 kg, \geq 70 kg, or not measured
BMI	Summary statistics
	<18.5 kg/m ² , <18.5 to 25 kg/m ² , <25 to 30 kg/m ² , \geq 30 kg/m ² , or unknown
Smoking history	Never, current, past, or unknown
Prior drug therapy	Absent or present

Data item	Category
Prior drug therapy regimen(s)	ABVD, CHOP, and/or other (If more than one drug therapies in the same category is used in the same patient, it will be counted as one patient.)
Number of prior drug therapy regimens	Summary statistics
Days from the month of the completion of the final regimen of prior drug therapy to the date of 1 cycle of treatment with Adcetris (Prior drug therapy: Yes)	Summary statistics
Prior radiotherapy	Absent or present
Days from the month of the completion of the most recent prior radiotherapy to the date of 1 cycle of treatment with Adcetris (Prior radiotherapy: yes)	Summary statistics
Prior hematopoietic stem cell transplantation	Absent, present (autologous), or present (homologous)
Other prior therapies	Absent or present
Pregnancy during the observation period (for females only)	Absent or present

(3) Figure/table number
Tables 3.0-1 to 3.0-3

4.0 Treatment Given

4.1 Treatment given

(1) Analysis sets to be used

Safety analysis set, safety analysis set (Hodgkin's lymphoma), and safety analysis set (anaplastic large-cell lymphoma)

(2) Data to be analyzed

For each data item, patients will be stratified into the following categories, and the number and frequency of patients will be calculated:

Data item	Category
Initial dose of Adcetris	1.8 mg/kg or other
Mean dose of Adcetris	<1.8 mg/kg, 1.8 mg/kg, or >1.8 mg/kg
Dose of Adcetris per 3 weeks	<1.8 mg/kg, 1.8 mg/kg, or >1.8 mg/kg
Duration of treatment with Adcetris	1, 2, 3, 4, 5, 6, 7, 8, 9, 10, 11, 12, 13, 14, 15, or 16 cycles
Reason(s) for discontinuation of Adcetris	Treatment goal achieved, adverse event(s), lost to follow-up, transfer to another hospital, pregnancy, inadequate response, and/or other
Post-baseline hematopoietic stem cell transplantation	Absent or present
Type of post-baseline hematopoietic stem cell transplantation	Autologous or homologous
Drug(s) other than Adcetris used for the treatment of the primary disease	Absent or present
Drug(s) used for the prevention of infection	Absent or present
Specific drug(s) used for the prevention of infection	Antibiotics/synthetic antibacterial agents, antifungals, antivirals, trimethoprim-sulfamethoxazole combinations, and/or other prophylactics against infections

(3) Figure/table number

Tables 4.1-1 to 4.1-3

4.2 Premedication to prevent infusion reaction

(1) Analysis sets to be used

Safety analysis set, safety analysis set (Hodgkin's lymphoma), and safety analysis set (anaplastic large-cell lymphoma)

(2) Data to be analyzed

For each cycle, patients will be stratified into the following categories, and the number and frequency of patients will be calculated:

Data item	Category
Premedication to prevent infusion reaction	Absent or present
Specific premedication(s) used to prevent infusion reaction	Acetaminophen, antihistamines, and/or corticosteroids

(3) Figure/table number

Tables 4.2-1 to 4.2-3

5.0 Safety Analysis

5.1 Occurrences of adverse events/infections and adverse drug reactions/infections

5.1.1 Occurrence of adverse events/infections

(1) Analysis sets to be used

Safety analysis set, safety analysis set (Hodgkin’s lymphoma), and safety analysis set (anaplastic large-cell lymphoma)

(2) Data to be analyzed

Data listed below will be analyzed.

For data entered in the field of “Adverse events: [1] Peripheral nerve disorders] in the case report form, MedDRA PT Code for peripheral sensory neuropathy, peripheral motor neuropathy, or peripheral neuropathy should be assigned, regardless of the LLT code entered in “Symptoms” field (see Section 1.1 ,the same applies hereinafter).

Neutrophil count decreased (PT Code 10029366) will be replaced by Neutropenia (PT Code 10029354), Lymphocyte count decreased (PT Code 10025256) by Lymphopenia (PT Code 10025327), White blood cell count decreased (PT Code 10047942) by Leukopenia (PT Code 10024384), and Platelet count decreased (PT Code 10035528) by Thrombocytopenia (PT Code 10043554) (the same applies hereinafter).

Data item	Data to be analyzed
Number of patients with adverse events, etc.	Number of patients experiencing adverse events, etc.
Number of adverse events, etc.	Number of adverse events, etc., observed If the same patient has multiple occurrences of the same adverse event, etc. (PT), the total number of occurrences will be calculated.
Percentage of patients with adverse events, etc.	Is calculated using the following formula: number of patients with adverse events, etc./number of patients included in the safety analysis set × 100.
Type of adverse events, etc.	Adverse events, etc., will first be classified by SOC, within each of which adverse events, etc., will be further classified by PT. Laboratory test data will first be classified by SOC, and will then be grouped into each HLGt and will be further classified by PT. For SOC, the number and percentage of patients with adverse events, etc., will be presented in the internationally agreed order. For PT, the number and percentage of adverse events, etc., will be presented in ascending order of PT codes. If the same patient has multiple occurrences of the same adverse event, etc. (PT), the event will be counted once per patient.

(3) Figure/table number

Tables 5.1-1 to 5.1.1-3

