#### 9.2.4 Tests and assessments

##### 9.2.4.1 Laboratory tests

###### 1) Outcome measures

Red blood cell count, hemoglobin level, white blood cell count, neutrophil count, lymphocyte count, platelet count, total bilirubin, AST, ALT, LDH, BUN, and serum creatinine

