**Table 1 Definition of an Adverse Event**

An adverse event (AE) is any untoward or undesirable medical occurrence in a patient linked in time with the use of a pharmaceutical/ medicinal product and which does not necessarily have to have a causal relationship with this treatment or may or may not be considered related to the product. An adverse event can therefore be any unfavorable and unintended sign (including an abnormal laboratory finding), symptom, or disease temporally associated with the use of a medicinal product, whether or not related to the medicinal product.

Adverse events also include:

- Symptoms observed in an infant breast-fed by a mother receiving treatment with Adcetris.

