5.0 Safety Analysis

5.1 Occurrences of adverse events and adverse drug reactions/infections

5.1.1 Occurrence of adverse events

(1) Analysis sets to be used

Safety analysis set, safety analysis set (Hodgkin’s lymphoma), and safety analysis set (anaplastic large-cell lymphoma)

(2) Data to be analyzed

Data listed below will be analyzed.

For data entered in the field of “Adverse events: [1] Peripheral nerve disorders] in the case report form, MedDRA PT Code for peripheral sensory neuropathy, peripheral motor neuropathy, or peripheral neuropathy should be assigned, regardless of data entered in “Symptoms” field (see Section 1.2, the same applies hereinafter).

MedDRA PT Code for “Infusion related reaction” should be assigned to the field of “Adverse events: [4] Infusion reaction” in the case report form, regardless of data entered in “Symptoms” field (see Section 1.2, the same applies hereinafter).

Neutrophil count decreased (PT Code 10029366) will be replaced by Neutropenia (PT Code 10029354), Lymphocyte count decreased (PT Code 10025256) by Lymphopenia (PT Code 10025327), White blood cell count decreased (PT Code 10047942) by Leukopenia (PT Code 10024384), and Platelet count decreased (PT Code 10035528) by Thrombocytopenia (PT Code 10043554) (the same applies hereinafter).

Data item	Data to be analyzed
Number of patients with adverse events	Number of patients experiencing adverse events
Number of adverse events	Number of adverse events observed. If the same patient has multiple occurrences of the same adverse event (PT), the total number of occurrences will be calculated.
Percentage of patients with adverse events	Is calculated using the following formula: number of patients with adverse events/number of patients included in the safety analysis set × 100.
Type of adverse events	The incidence of adverse events will be calculated by SOC and PT. For SOC, the number and percentage of patients with adverse events will be calculated. For PT, the number and percentage of adverse events will be calculated. SOCs will be presented in the internationally agreed order, and PTs will be presented in ascending order of HLGT and PT codes if their SOCs are “Investigations,” and in ascending order of PT code otherwise. If the same patient has multiple occurrences of the same adverse event (PT), the event will be counted once per patient.

(3) Figure/table number

Tables 5.1-1 to 5.1.1-3

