5.0 Safety Analysis

5.1 Occurrences of adverse events/infections and adverse drug reactions/infections

5.1.1 Occurrence of adverse events/infections

(1) Analysis set to be used

Safety analysis set

(2) Data to be analyzed

Data listed below will be analyzed.

For data entered in the field of “Adverse events: [1] Peripheral nerve disorders] in the case report form, MedDRA PT Code for peripheral sensory neuropathy, peripheral motor neuropathy, or peripheral neuropathy should be assigned, regardless of the LLT code entered in “Symptoms” field (see Section 1.1 “Definition;” the same applies hereinafter).

Neutropenia (PT Code 10029354) will be assigned to Neutrophil count decreased (LLT Code 10029366), Lymphopenia (PT Code 10025327) to Lymphocyte count decreased (LLT Code 10025256), Leukopenia (PT Code 10024384) to White blood cell count decreased (LLT Code 10047942), and Thrombocytopenia (PT Code 10043554) to Platelet count decreased (LLT Code 10035528) (the same applies hereinafter).

Data item	Data to be analyzed
Number of patients with adverse events, etc.	Number of patients experiencing adverse events, etc.
Number of adverse events, etc.	Number of adverse events, etc., observed. If the same patient has multiple occurrences of the same adverse event, etc. (PT), the total number of occurrences will be calculated.
Percentage of patients with adverse events, etc.	Is calculated using the following formula: number of patients with adverse events, etc./number of patients included in the safety analysis set × 100.
Type of adverse events, etc.	Adverse events, etc., will first be classified by SOC, within each of which adverse events, etc., will be further classified by PT. Laboratory test data will first be classified by SOC, and will then be grouped into each HLG and will be further classified by PT. For SOC, the number and percentage of patients with adverse events, etc., will be presented in the internationally agreed order. For PT, the number and percentage of adverse events, etc., will be presented in ascending order of PT codes. If the same patient has multiple occurrences of the same adverse event, etc. (PT), the event will be counted once per patient.

(3) Figure/table number

Table 5.1-1

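### The blood-count recoding in final SAP 5.1.1 has no rule for haemoglobin or red-cell laboratory terms, so anaemia may be spread over separate rows if such terms are reported

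*SAP*

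**What the plan says.** The SAP file holds three versions of the plan and two supplements. The operative text is the version that defines the analysis sets in 1.1 and refers to the Final Survey Report in 1.6, called the final SAP here.

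Final SAP 5.1.1 merges laboratory and clinical wording for four blood counts:

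- neutrophils: "Neutrophil count decreased (PT Code 10029366) will be replaced by Neutropenia (PT Code 10029354"
- lymphocytes: "Lymphocyte count decreased (PT Code 10025256) by Lymphopenia (PT Code 10025327"
- white cells: "White blood cell count decreased (PT Code 10047942) by Leukopenia (PT Code 10024384"
- platelets: "Platelet count decreased (PT Code 10035528) by Thrombocytopenia (PT Code 10043554) (the same applies hereinafter"

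The closing words of the last item carry the rule into every later table. Section 5.1.1 also says how PTs under the Investigations organ class are ordered ("PTs will be presented in ascending order of HLGT and PT codes if their SOCs are"), so the tables leave room for laboratory-type terms that are not replaced. At PT level, repeated occurrences in one patient count once, but only within the same PT.

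Protocol 9.2.4.1 lists the blood counts collected: "Red blood cell count, hemoglobin level, white blood cell count, neutrophil count, lymphocyte count, platelet count". Protocol Table 1 makes an adverse event include "any unfavorable and unintended sign (including an abnormal laboratory finding), symptom, or disease temporally associated with the use of a medicinal product".

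**The concern.** The replacement rule exists because one toxicity can reach the database in two wordings, a fall in a count or a named cytopenia. Merging them gives one row, one count per patient and one worst grade per patient. The plan does this for four of the six blood counts it collects. It does not do it for haemoglobin and red cell count, and it gives no reason.

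If investigators report some red-cell falls as laboratory findings and others as anaemia, these would stand in different rows. A reader of 5.1.1, 5.1.2 or 5.7 who looks up anaemia would see only part of the affected patients. Tables 5.2.2 and 5.2.4 take the highest CTCAE grade once per patient within a PT. A patient with Grade 2 anaemia and a separately recorded Grade 3 haemoglobin fall would therefore count as Grade 2 or lower in the anaemia row. Sections 5.4 to 5.6 reuse the 5.1 method and would inherit the gap.

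The study's purpose is safety (protocol 2.0), and protocol 14.1 commits the sponsor to watch for rising frequency of particular reactions. Frequencies by term are what such monitoring uses.

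**Working it through.** The plan gives no anaemia incidence and names no red-cell event term, so there is no figure to reproduce. The check compares the texts and then gives an illustration.

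**Step 1. Tests collected against replacements given.**

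| Blood count in protocol 9.2.4.1 | Replacement in final SAP 5.1.1 |
|---|---|
| Neutrophils | Neutropenia |
| Lymphocytes | Lymphopenia |
| White cells | Leukopenia |
| Platelets | Thrombocytopenia |
| Haemoglobin | none |
| Red cells | none |

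**Step 2. Is the missing pair elsewhere?** No. The next version in the file has the same four pairs in its 5.1.1. The one after that has them with the laboratory terms labelled as LLTs, ending "Thrombocytopenia (PT Code 10043554) to Platelet count decreased (LLT Code 10035528) (the same applies hereinafter", and again no red-cell pair. The first supplement defines neutropenia and lymphopenia so that each takes in both wordings. The second repeats the neutrophil replacement. Neither mentions haemoglobin or red cells.

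**Step 3. Can the published rows be combined?** Not for patient counts. De-duplication stops at the PT, so a patient recorded under both wordings stands in two rows. Using the anaemia row alone can undercount, and adding the rows can overcount.

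**Step 4. Illustration.** Take N = 140 (protocol 3.1) as the denominator. Assume T = 20 patients with any red-cell event, a share s of them recorded only under a laboratory PT, and b patients recorded under both. T, s and b are assumptions; the documents give none of them.

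- Anaemia row = (T − sT)/N
- Laboratory row = (sT + b)/N
- Sum of rows = (T + b)/N
- True incidence = T/N = 20/140 = 14.3%

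| s | Patients in anaemia row | Anaemia row |
|---|---|---|
| 0% | 20 | 20/140 = 14.3% |
| 25% | 20 − 5 = 15 | 15/140 = 10.7% |
| 50% | 20 − 10 = 10 | 10/140 = 7.1% |

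At s = 0 nothing is lost. If b = 4 (20% of the 20), the two rows add to 24/140 = 17.1% against a true 14.3%.

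**Step 5. What does not move.** The percentage of patients with any adverse event in 5.1.1 counts a patient whichever term is used, so it is the same under every s and b. The five events of particular interest (protocol 9.2.5) do not include anaemia.

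**The case against.** The strongest reply is that the effect is conditional and nothing shows the condition is met. No document says that a haemoglobin or red-cell laboratory term was reported. If every site writes anaemia, the missing pair changes no table. This stands, and it is why the range above starts at zero.

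Second, the asymmetry may be deliberate. Neutropenia is an event of particular interest with its own analyses in final SAP 5.9.7 to 5.9.9, and lymphopenia is used in the infection-timing analysis of the first supplement. Anaemia has neither role. This is a partial answer only, because it does not explain why white cells and platelets are replaced.

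Third, no data are lost. A red-cell laboratory term would still appear as its own row, the sponsor holds patient-level data, and final SAP 5.8.1 summarises haemoglobin and red cell count by cycle, with box plots for haemoglobin. This stands as far as it goes: a general fall in haemoglobin would be visible. But those summaries give no patient incidence, causality, seriousness or outcome, and a reader of the tables cannot rebuild a per-patient count.

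A reader might infer more, namely that anaemia is in fact split over two organ classes and its incidence is understated. The documents do not support that. They name no red-cell event term, and the organ class of such a term is settled by the MedDRA dictionary, not by the plan.

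**Conclusion.** The omission is real and is the same in all three versions of the SAP. Its consequence is only possible. If red-cell falls are reported under laboratory PTs, the anaemia row and its worst-grade count may be too low, and the published patient counts cannot be added. The size is unknown and may be zero. The illustrative values of 14.3%, 10.7% and 7.1% rest on an assumed 20 affected patients out of 140 and assumed shares of 0%, 25% and 50% recorded only under a laboratory term. This is a minor point of consistency in single rows, and it leaves the study's headline safety figures as they are. It is worth making because the sponsor already accepts the principle for four counts and the remedy is very cheap.

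**What to change.** Add one replacement to the rule in final SAP 5.1.1: any PT for decreased haemoglobin or decreased red blood cell count will be replaced by Anaemia, in that table and all later ones, on the same terms as the other four. The PT codes should be taken from MedDRA version 19.1, which final SAP 1.6 specifies, since the documents do not give them.

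The cost is one sentence and one line of recoding. If no such terms occur, no result changes. If they do, each patient has one red-cell count and one worst grade. The downside is that red-cell laboratory terms no longer have rows of their own, a loss already accepted for the other four counts.
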